13.2. Secondary efficacy

Secondary efficacy endpoints will be on ITT population.

13.2.1. Secondary efficacy variables & derivations

Change in LogMAR BCVA

The first secondary efficacy endpoint is the change from baseline in LogMAR BCVA to each follow-up visit (after 1.5 years) (see section 13.1.4) with the same missing data imputation strategy.

For 5-year analysis, additional supportive analyses will be done:

- Using last available LogMAR value
- Same analysis on PP5Y population.

Response status

The second secondary efficacy endpoint is the responder rate.

For subjects discontinued prior to the time of analysis or with missing data, LOCF imputed data will be used.

Three definitions of responders are given below:

Definition 1 – Gainer eyes:

Eyes whose LogMAR BCVA improves (i.e. decrease) by ≥ 0.3 LogMAR (equivalent to a gain of ≥ 15 ETDRS letters) compared to baseline, i.e. an eye is a responder if: $\text{LogMAR at interest timepoint} - \text{LogMAR at Baseline} \leq -0.30$.

Definition 2 – Stabilized eyes:

Eyes whose LogMAR BCVA does not worsen (i.e. does not increase) by ≥ 0.3 LogMAR (equivalent to an eye that loses ≤ 15 ETDRS letters) compared to baseline, i.e. an eye is a responder if: $\text{LogMAR at interest timepoint} - \text{LogMAR at Baseline} \leq 0.30$.

Definition 3 - Not legally blind:

Eyes whose LogMAR visual acuity is < 1.0 at interest timepoint (i.e. better than LogMAR 1.0, equivalent to better than Snellen acuity of 20/200).

This third definition of interest is exploratory given the precipitous vision loss experienced by the majority of ND4 LHON subjects. Any significant difference in the percentage of second-affected/not-yet-affected responder eyes, receiving GS010 compared to placebo, is pertinent considering the seriousness of the visual impairment.

The response status will be assessed at eye and subject level.

For subject response, the best response observed in either eye will be considered (LogMAR measured on both eyes will not be considered).

Parameters measured with SD-OCT

The changes from baseline at each time point in the following parameters as measured by the SD-OCT:

- Total and Temporal Quadrant Retinal Nerve Fiber Layer (RNFL) thickness;
- Papillo Macular Bundle (PMB) RNFL thickness
- Ganglion Cell Layer macular volume
- ETDRS macular volume

HVF 30-2

The changes from baseline at each time point the following parameters of standardized, automated visual fields obtained with the HVF Analyzer II (HVF 30-2):

- Mean deviation
- Foveal threshold sensitivity
- Pattern standard deviation

If HVF is off then set to missing, if <0 set to 0.

The changes over time of each data point of HVF, with the following thresholds of gain or loss: ≥ 7 dB; 5-6.99 dB; 3-4.99 dB; ≤ 2.99 dB. Graphic mapping of HVFs per eye and per patient will be provided. Only reliable HVFs will be included in this analysis.

Contrast sensitivity measured with the Pelli-Robson Low Vision Contrast Sensitivity.

The last set of the 3rd secondary efficacy endpoint is the change from baseline at each time point in low vision contrast sensitivity as measured by the Pelli-Robson chart.

On-chart and off-chart contrast sensitivity

The Contrast Sensitivity score is calculated based on the last triplet of letters for which at least two of the three letters were read correctly (any result obtained past the triplet where the patient could not read at least 2 letters correctly is not to be recorded as the result). On-chart subjects are able to read at least two letters of the first triplet of the Pelli-Robson chart, and will thus have a CS value expressed in LogCS. Off-chart subjects are not able to read at least two letters of the first triplet of the Pelli-Robson chart, and will thus have no CS value. As no equivalent score exists for off-chart LogCS, 0 be assigned for eyes with off-chart LogCS.

Same analyses will be conducted on the LogCS instead of the change of LogCS for all eyes.

Quality of Life assessments

Visual Functioning Questionnaire-25

The VFQ-25 Questionnaire is a 25-item version of the 51-item National Eye Institute Visual Function Questionnaire. The VFQ-25 consists of a base set of 25 vision-targeted questions representing 11 vision-related constructs, plus an additional single-item general health rating question. All items are scored from 0 to 5 so that a higher number represents better functioning. To score the questionnaire, each item is converted to a 0-100 scale. Items within each subscale are averaged to create 12 subscale scores. The subscale scores (excluding the general health rating question) are then averaged to calculate the composite score (Mangione 2001), subscales with at least one item answered can be used to generate a sub-scale score. Hence, scores represent the average for all items in the sub-scale that the respondent answered. Items that are left blank (missing data) are not taken into account when calculating the scale score.

By averaging the subscale scores rather than the individual items it will give equal weight to each subscale, whereas averaging the items would give more weight to scales with more items.

The secondary efficacy endpoint for VFQ-25 will be the change from baseline in the VFQ-25 composite score to each post-treatment follow-up visit.

Details of the conversion scale, sub-scales, calculations of the subscale scores and formula for averaging the subscale scores can be found in Appendix 4.

36-Item Short Form Health Survey, Version 2

The SF-36 Questionnaire is a generic, subject-reported outcome instrument used to assess QoL. The SF-36 is a 36-question instrument, which assesses 8 health concepts:

1. limitations in physical activities because of health problems;
2. limitations in social activities because of physical or emotional problems;
3. limitations in usual role activities because of physical health problems;
4. bodily pain;
5. general mental health (psychological distress and well-being);
6. limitations in usual role activities because of emotional problems;
7. vitality (energy and fatigue);
8. general health perceptions.

The scale score of each domain is calculated based on the summed score across items included in the domain and is rescaled to 0 to 100 with higher scores indicating better health states. The rescaled score of each domain is then normalized for the US population. Finally, the Physical Component Score (PCS) and Mental Component Score (MCS) will be computed using the normalized domain scores (Ware 2007).

Items that are left blank (missing data) are not taken into account when calculating the scale scores. Hence, scale scores represent the average for all items in the scale that the respondent answered.

The secondary efficacy endpoints for the SF-36 will be the change from baseline in each of the SF-36 domains as well as in the two composite scores to each post-treatment follow-up visit.

Details of the conversion rules, transformation scales, scale raw score range and scoring rules for overall component can be found in Appendix 5.

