### 12.5.2 Visual Acuity

Visual acuity will be assessed at each visit per the study schedule, after refraction. Eligible subjects will include those with eyes able to read letters on the Early Treatment Diabetic Retinopathy Study (ETDRS) chart, defined as on-chart eyes, and eyes unable to read letters on the ETDRS chart, defined as off-chart eyes. Please refer to the SOP for Ocular and Vision Testing for the detailed definition of off- and on-chart eyes.

On-chart eyes are able to read at least 3 letters on the ETDRS chart at 1 meter distance and will thus have an ETDRS score, Snellen BCVA and LogMAR BCVA based on the letters/lines read on the ETDRS chart at 4 and 1 meters' distance.

Off-chart subjects are not able to read at least 3 letters on the ETDRS at 1 meter distance and thus will have an ETDRS score but will not have Snellen visual acuity or LogMAR acuity obtainable based on the number of ETDRS letters/lines read. Off-chart subjects will be tested for count fingers (CF) or hand motion (HM) visual acuity per the SOP for Ocular and Vision Testing.

LogMAR visual acuity will be obtained for off-chart eyes based on Karanjia et al. 2014 (Karanjia 2014). Please see the SOP for Ocular and Vision Testing for full details. Briefly, the finger/hand dimensions of the examiner will be measured. The examiner will present the fingers/hand to assess CF or HM vision and will measure the distance at which the subject accurately counted fingers or detected HM. The finger/hand dimensions of the examiner and the distance at which CF or HM was performed will be entered into the equation utilized by Karanjia et al. 2014, modified for assessment of visual acuity in meters. The output of interest is the LogMAR BCVA.

For the purposes of the study 1 ETDRS line / 5 ETDRS letters is considered equivalent to 0.1 LogMAR and 1 ETDRS letter is equivalent to 0.02 LogMAR.

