#### *LogMAR:*

Three definitions of responders for LogMAR are given in Section 8.2 where the first definition is the most important. The first responder definition (Gainer eyes) is an eye whose LogMAR BCVA improves (i.e. decreases) by  $\geq 0.3$  LogMAR:

LogMAR at 1-5 years – LogMAR at Baseline  $\leq -0.30$  = responder eye.

A logistic regression, with adjustment for baseline, will be performed to compare differences in responder rates. An odd ratio less than 0.8 between treatment groups will be considered as a clear clinically pertinent effect. An interaction with region will be assessed. The second definition of responder (“Stabilized eyes”) is an eye whose LogMAR BCVA does not worsen (i.e. does not increase) by  $\geq +0.3$  LogMAR:

LogMAR at 1.5 Years – LogMAR at Baseline  $\leq +0.30$  = responder eye.

The third definition of interest is exploratory given the precipitous vision loss experienced by the majority of ND4 LHON subjects. The third definition of responder eye is an eye whose LogMAR visual acuity is better (i.e. lower) than 1.0 (i.e. equivalent to being better than a Snellen acuity of 20/200). Any significant difference in the percentage of second affected/not yet affected responder eyes, receiving GS010 compared to placebo, is pertinent considering the seriousness of the visual impairment. The same analysis as for the first responder definition will be performed for the second and third definitions of responder.

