6.0 26OCT2020		Updated efficacy and safety sections and add of Natural history SAP in appendix 6.
7.0 14APR2021		Updated after dry-run.
8.0 03MAY2021		Modification of LogMAR calculation: The LogMAR values for CF and HM based on the Karanjia equation; will not be used for analyses due to the difficulties encountered in measuring the scale parameters on the clinical sites: The parameters measured for the calculation of the Karanjia LogMAR were not recorded accurately by the clinical centers:

		
 Difficulties in the adherence to the parameters measurements described in the SOP Errors in the conversion of the reading distances, finger and interdigital widths from US metric to EU metric system, leading to unreliable measurements. 
It is decided to only use the validated Lange LogMAR assignments to count fingers (CF) or hand motion (HM) visual acuity (C. Lange et al. Graefes Arch Clin Exp Ophthalmol (2009) 247:137-142)..

9.0 26OCT2021		
 Error in the SF-36 calculation, add 1 step: Transform composite scores PCS and MCS and 8 Z-score to Normalized scores = 50 + (Health Domain Z-score × 10) (see end of APPENDIX 4. Scoring rules for multi-item scales in SF-36 (Ware 2007) Modification of prior / concomitant medication definitions: see Changes to analysis from protocol (7)
9.1 17FEB2023		
 Update of time windows definition to follow Data review decision for 1.5-year analysis. Modification of data missing handle
9.2 17SEP2024		Update following [name] review before final analysis
9.3 09OCT2024		Update following DRM of 25SEP2024
10.0 10OCT2024		Final version before database lock

Approvals

Date of Data Review: 25SEP2024

Name	Position	Date	Signature
GENSIGHT			
			
eXYSTAT			
			

Table of Contents

1. INTRODUCTION	12
2. STUDY OBJECTIVES	12
2.1. PRIMARY OBJECTIVE	12
2.2. SECONDARY OBJECTIVES	12
3. STUDY DESIGN	13
3.1. GENERAL DESCRIPTION	13
3.2. SAMPLE SIZE CONSIDERATION	16
3.3. SCHEDULE OF EVENTS	16
3.3.1. STUDY SCHEDULE	17
3.3.2. STUDY DURATION	18
3.4. CHANGES TO ANALYSIS FROM PROTOCOL	18
3.5. DATA SAFETY MONITORING BOARD	19
3.6. PRIMARY EFFICACY ANALYSIS	19
3.7. POST-TREATMENT FOLLOW-UP PERIOD ANALYSES	20
4. ANALYSIS POPULATIONS	20
4.1. ALL SUBJECTS ENROLLED SET	20
4.2. INTENT-TO-TREAT POPULATION	20
4.3. MODIFIED INTENT-TO-TREAT POPULATION	20
4.4. PER PROTOCOL POPULATION	20
4.5. PER PROTOCOL-5Y POPULATION (PP5Y)	20
4.6. SAFETY ANALYSIS POPULATION	20

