13.1.1. Primary efficacy variable & derivation

Visual acuity (EDTRS and LogMAR)

ETDRS score is calculated by the examiner and written on the source documents and entered in the eCRF.

One Early-Treatment Diabetic Retinopathy Study (ETDRS) line equates to 0.1 LogMAR, and 1 ETDRS letter equates to 0.02 LogMAR.

On chart and off chart

On-chart subjects are able to read at least three ETDRS letters on a single line of the ETDRS chart at 1 meter distance and will thus have an ETDRS score, Snellen visual acuity, and LogMAR visual acuity based on the letters/lines read on the ETDRS chart at 4- and 1-meter distances.

Off-chart subjects are not able to read at least three ETDRS letters on a single line of the ETDRS chart at 1 meter distance and thus will not have an ETDRS score. Off-chart subjects will be tested for count fingers (CF) or hand motion (HM) visual acuity per the SOP for Ocular and Vision Testing. The LogMAR visual acuity will be assigned to the validated Lange scale LogMAR value for CF and HM (C. Lange et al. Graefes Arch Clin Exp Ophthalmol (2009) 247:137-142):

- +2.0 LogMAR for CF
- +2.3 LogMAR for HM

For light perception (LP) +4.0 LogMAR is assigned

For no light perception (NLP) +4.5 LogMAR is assigned.

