13.3. Other efficacy

Nadir for LogMAR BCVA and for LogCS

Nadir of BCVA/LogCS is defined for each eye of each subject as the worst value observed from baseline to the post-treatment timepoint of interest, including baseline and the post-treatment timepoint values.

For LogCS only, if there is at least one value off-chart between baseline and timepoint, then Nadir cannot be calculated as no off-chart value exists; off-chart LogCS will be imputed a value of 0.

If there are more than one off-chart value from baseline to the timepoint of interest, then the first value over time will be considered the nadir. If there is more than one worst value from baseline to the point of interest (i.e. identical worst values occurring more than once), then the first value over time will be considered the nadir.

The change from Nadir BCVA/LogCS will be calculated for each eye of each subject and will be analyzed as primary endpoint (see section 13.1.4).

The time to Nadir BCVA/LogCS will be calculated for each eye of each subject and will be expressed in Weeks. This analysis will be only descriptive.

Clinically Relevant Recovery (CRR)

At the eye level, a CRR from baseline is defined as:

- For eyes on-chart at baseline, an improvement of at least -0.2 LogMAR
- For eyes off-chart at baseline, eyes which became on-chart.

On-chart value is defined as \leq LogMAR 1.6

Subject with CRR from baseline is defined as subject with a CRR in at least one eye: Subject with at least one eye which was on chart at baseline, and which had an improvement of at least -0.2 LogMAR from baseline, or which was off-chart at baseline but became on-chart.

Subjects with CRR from baseline will be assessed for all subjects, bilaterally GS010 treated subjects and unilaterally GS010 treated subjects.

At the eye level, a CRR from nadir is defined as:

- For eyes on-chart at nadir, an improvement of at least -0.2 LogMAR from nadir
- For eyes off-chart at nadir, eyes which became on-chart.

Subject with CRR from nadir is defined as subject with a CRR in at least one eye: Subject with at least one eye which was on chart at nadir, and which had an improvement of at least -0.2 LogMAR from nadir, or which was off-chart at nadir but became on-chart.

Subjects with CRR from nadir will be assessed for all subjects, bilaterally GS010 treated subjects and unilaterally GS010 treated subjects.

These responder endpoints will be analyzed as section 13.2.3

Other responses parameters

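### With fixed off-chart values, a change from hand motion to count fingers is exactly -0.30 LogMAR, so Definition 1 counts an eye that is still off-chart as a gainer of 15 or more letters

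*SAP*

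**What the plan says.** **Responder rule.** SAP 13.2.1, Definition 1, covers "Eyes whose LogMAR BCVA improves (i.e. decrease) by" 0.3 LogMAR or more, and glosses this as "equivalent to a gain of ≥ 15 ETDRS letters) compared to baseline, i.e. an eye is a responder if" the change from baseline is -0.30 or lower. The boundary is included. There is no exception for off-chart eyes. Protocol 16.4.2.1 lists three responder definitions, "where the first definition is the most important". At subject level the better response of the two eyes counts. SAP 13.3 applies the same 0.3 cut-off to change from nadir.

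**Off-chart values.** In Protocol 12.5.2 the off-chart LogMAR came from the examiner's finger or hand dimensions and the test distance: the examiner "will measure the distance at which the subject accurately counted fingers or detected HM". The SAP version history (8.0, "Modification of LogMAR calculation") drops that method because sites did not record the inputs reliably. SAP 13.1.1 now assigns "2.0 LogMAR for CF" and "2.3 LogMAR for HM", with 4.0 for light perception (LP) and 4.5 for no light perception (NLP). The same section says that off-chart subjects have no ETDRS score.

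**The other response measure.** For CRR, SAP 13.3 applies a separate rule to off-chart eyes: "For eyes off-chart at baseline, eyes which became on-chart". On-chart there means LogMAR 1.6 or lower.

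**Eligibility.** HM is the floor for inclusion (Protocol 10.2.3). LP and NLP are excluded at Visit 2 (Protocol 10.2.4).

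**The concern.** The 0.3 threshold was set when an off-chart eye had a value that varied with test distance. It was kept when that scale was replaced by fixed categories. The gap between the two categories an eligible off-chart eye can have at baseline now equals the threshold, so a one-category change is enough for response under the definition the protocol ranks highest.

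The letter label does not fit these eyes, because by SAP 13.1.1 they have no letter score at either time point. The same eye is a gainer in 13.2.1 and not recovered in 13.3. A reader of the gainer rate will take it as letters gained and cannot tell how much of it is HM to CF. The planned outputs do not show this either: in the on-chart/off-chart shift tables an HM-to-CF eye sits in the off-to-off cell, and CRR leaves it out without a count.

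Because the change falls exactly on the cut-off, the result also depends on how the subtraction is programmed.

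**Working it through.** **Inputs.** CF 2.0, HM 2.3, LP 4.0, NLP 4.5, and 0.02 LogMAR per letter (SAP 13.1.1). Cut-off -0.30, inclusive (SAP 13.2.1). On-chart at 1.6 or lower (SAP 13.3). 45 evaluable subjects per arm (SAP 3.2).

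**1. The plan's equivalence.** 15 letters x 0.02 = 0.30 LogMAR. The stated conversion reproduces.

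**2. Changes from off-chart baselines**

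| Change | LogMAR change | Definition 1 | CRR |
|---|---|---|---|
| HM to CF | 2.0 - 2.3 = -0.30 | yes | no |
| CF to 1.6 | 1.6 - 2.0 = -0.40 | yes | yes |
| HM to 1.6 | 1.6 - 2.3 = -0.70 | yes | yes |

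Only HM to CF separates the two measures here. Requiring on-chart status removes that row and keeps every gain that reaches the chart.

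**3. From nadir.** Nadir can fall after baseline, so LP and NLP are possible reference values. HM to CF (-0.30), LP to HM (2.3 - 4.0 = -1.70) and NLP to LP (4.0 - 4.5 = -0.50) all meet the 0.3-from-nadir rule with the eye still off-chart.

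**4. Size.** One eye is 1/45 = 2.2 percentage points of an arm's rate. The documents give neither the share of eyes at HM nor the share of those that later score CF. As pure assumptions, with 5% to 30% at HM and 10% to 50% of those reaching CF:

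- low: 0.05 x 0.10 = 0.5 points
- high: 0.30 x 0.50 = 15 points

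The range is wide because nothing in the documents narrows it.

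**5. Arithmetic at the boundary.** In double precision 2.0 - 2.3 evaluates to -0.2999999999999998, so the test for -0.30 or lower is false. The written rule counts the eye; unrounded code does not. Rounding the change to two decimals restores agreement. Appendix 1 of the SAP has rounding rules for displayed statistics only.

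On-chart eyes can be affected too. Assume LogMAR = 1.70 - 0.02 x letters (the 1.70 is not in the documents) and take exact 15-letter gains from starting scores 3 to 85. Then 22 of 83 fail the unrounded test. If each LogMAR value is first rounded to two decimals but the difference is not, 17 of 83 fail. If the difference is rounded, none fail.

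**The case against.** **What stands**

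- The endpoint is secondary, and SAP 6.3 spends all alpha on the primary endpoint.
- Off-chart responders were always possible: the protocol's distance-based scale had no on-chart requirement either. Fixed values create one certain step but remove every gain within CF or within HM. A reader might infer that the change of scale raised the number of off-chart responders. The documents do not show whether it rose or fell.
- CRR, the 1.6 and 1.0 acuity responders and the shift tables already describe off-chart eyes in other ways. A difference between CRR and Definition 1 can be read as two complementary endpoints, so it is not in itself an error.
- The 1.5-year analysis is past (SAP 5.3 refers to visits made after it). Replacing a protocol-specified definition now would be an endpoint change after unmasking.

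**Stronger readings that the documents do not support**

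- That HM to CF is measurement noise and these are false responders. Neither document gives repeatability data for these categories, and the SAP calls the scale validated.
- That these eyes cannot read a letter. SAP 13.1.1 defines off-chart as fewer than three letters on one line at 1 metre. Protocol 12.5.2 says that off-chart subjects do have an ETDRS score, so the absence of a letter score rests on the SAP alone.
- That the rule favours GS010. Nothing shows more HM-to-CF eyes in one arm than in the other.
- That the effect can be judged against the 14.7% of eyes with a 15-letter gain in the natural-history study cited in Protocol 6.1. How that study scored off-chart eyes is not stated.

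**What does not answer the point.** None of the planned outputs shows how many Definition 1 responders are HM-to-CF eyes. Calling 15 letters a unit conversion does not help the reader of a rate labelled as letters gained. The programming issue is real although no code for this derivation is shown, because the written rule and unrounded code give opposite answers for the same eye.

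**Conclusion.** The point holds in this form. Under SAP 13.1.1 and 13.2.1, an eye that moves from HM to CF meets Definition 1 exactly at its boundary while still off-chart. It is labelled a gain of 15 or more letters although the SAP gives it no letter score and CRR would not count it. This follows from the written values and needs no assumption.

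The number of such eyes is unknown: 2.2 percentage points per eye per arm, and 0.5 to 15 points under the assumed shares above. The finding limits what the gainer rate can be said to show. It does not touch control of the primary type I error, and it is no evidence of bias between arms. The plan should be changed by addition, since the documents do not justify redefining the endpoint.

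**What to change.** Keep Definition 1 as specified and add three things to the SAP.

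1. **Sensitivity version.** For Definition 1 and for the 0.3-from-nadir responder, count an eye that is off-chart at the reference point (baseline or nadir) only if it is on-chart at the time point. Use the 13.3 rule (LogMAR 1.6 or lower), and report at eye and subject level. On-chart eyes keep the 0.3 rule.
2. **Separate count.** Report by arm how many Definition 1 responders are HM-to-CF eyes, and do not describe them as 15-letter gains.
3. **Rounding.** Round the LogMAR change to two decimals before applying any threshold.

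Leave the 0.2-from-baseline responder as it is. With an on-chart condition it would become CRR from baseline: a 0.2 gain for on-chart eyes, and reaching the chart for off-chart eyes.

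The cost is one extra responder table, a few sentences of SAP text and one programming condition, with no new data. Rates in the sensitivity version will be somewhat lower than under Definition 1 if any HM-to-CF eyes exist.

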LHON manifests as acute to sub-acute, sequential, bilateral, painless vision loss. It is a bilateral disease and clinical manifestation is essentially predictive of bilateral involvement. Greater than 97% of subjects are reported to have bilateral involvement at 12 months and occurrences of unilateral involvement in retrospective reports of cohorts with LHON are very rare (Newman 1991, Riordan-Eva 1995). Lam et al. (Lam 2014) reported a G11778A *ND4* cohort in which 53% reported bilateral involvement in  $\leq 2$  months and 80% reported bilateral involvement in  $\leq 6$  months.

The clinical hallmark of LHON is central vision loss (Sadun 2011). This is accompanied by dysfunction of color and contrast vision and central and cecocentral visual field defects. Newman et al. (Newman 1991) reported a final visual acuity of 20/200 or worse in 98% of eyes. Lam et al. (Lam 2010, Lam 2014) performed a prospective natural history study of LHON subjects with the G11778A *ND4* mutation. The primary outcome was the finding of no significant difference in

ETDRS visual acuity at 12, 24 or 36 months of follow-up compared to baseline at study entry. This finding was for the entire cohort as well as for the subgroups of subjects who entered the study within 12 months of disease onset or after 12 months of disease onset. 14.7% of total study eyes, in 18% of study subjects, had improvement by  $\geq 15$  ETDRS letters over the study period. Eighty-six percent of subjects had eyes with stable acuities during study follow-up. Subjects entering the study after 36 months from disease onset showed no change or improvement of visual acuity over follow-up. The authors concluded that for G11778A *ND4* mutation spontaneous natural recovery is partial and occurs on a very limited basis in a small percentage of subjects and thus gene therapy interventions can be measured for efficacy with a reasonable sample size.

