#### 12.5.4 Humphrey Visual Field 30-2

Standard, automated perimetry will be obtained with the an HVF Analyzer II (Carl Zeiss Meditec Inc.) using the 30-2 SITA Fast strategy, Stimulus III White, per the study schedule. Details of the examination procedure will be provided in the SOP for Ocular and Vision Testing. A central reading center will perform quality control, analysis and interpretation of all HVF.

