#### *16.4.2.2 Parameters measured with SD-OCT, HVF and contrast sensitivity*

Parameters of SD-OCT (e.g. Total and Temporal Quadrant RNFL thickness, GCL volume and thickness and other parameters measured by SD-OCT), parameters of standardized, automated visual fields obtained with HVF Analyzer II (HVF 30-2) (e.g. mean deviation, foveal threshold sensitivity, pattern standard deviation and others), and contrast sensitivity measured with the Pelli-Robson Low Vision Contrast Sensitivity, will be used as secondary endpoints.

These parameters will be analyzed separately using a MMRM model. The MMRM model will include the appropriate baseline measurement as a covariate; stratification factor, treatment group, time point, and treatment group-by-time point interaction as fixed effects; and subjects as random effect. A first-order autoregressive (AR(1)) covariance structure will be used to model the within-patient error and the Kenward-Roger approximation will be used to estimate the degrees of freedom. If this analysis fails to converge, the following covariance structure will be tested one after the other in that order until one converge (remaining covariance structures will not be tested): ARH(1), CS, CSH, TOEP, and TOEPH.

Adjusted difference between the treatment groups will be estimated at each post-treatment time point, along with the two-sided 95% CI and p-value.

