13.2.3. Analysis of Secondary Efficacy Variables

Change in LogMAR BCVA analysis

Change in LogMAR compared to baseline, at each timepoint of the Follow-Up Period up to 5 years post- treatment will be analyzed at each visit using separate ANCOVA models as primary endpoint (see section 13.1.4).

Response status

For each response parameter and at each timepoint of the Follow-Up Period up to 5 years post- treatment, logistic model, including a factor for treatment group and the baseline value as a covariate will be considered on:

- Second-affected eye at timepoint (at eye level)
- First-affected eye at timepoint (at eye level)
- First and second affected eye at timepoint (at subject level): best response between both eyes

SAS code:

```
ARM=subject Treatment arm (1=GS010 – 0=Placebo); resp=responder variable; Logmar0=Logmar at baseline;
proc logistic data=XXX;
class ARM;
model resp=logmar0 ARM;
run;
```

For each of the response definitions and at each timepoint of the Follow-Up Period up to 5 years post- treatment, a logistic model, including a factor for treatment group, eye, the baseline value as a covariate, will be fit using GLMM for first and second affected eye at timepoint (at eye level)

SAS code:

```
ARM=subject Treatment arm (1=GS010 – 0=Placebo); resp=responder variable; Logmar0=Logmar at baseline;
proc glimmix data=XXX_ana;
class ID ARM;
model resp= ARM logmar0 /dist=bin solution cl;
random intercept/sub=ID type=ar(1);
run;
```

Parameters measured with SD-OCT, HVF and contrast sensitivity

The parameters detailed in sections 13.2.1 will be analyzed separately using a MMRM model, with adjustment for baseline score, as described in section 13.1.6.

Quality of Life assessments

Visual Functioning Questionnaire-25 (VFQ-25)

VFQ25 measures will be assessed at the subject level, looking at change from baseline for all subjects and comparing the change from baseline between the two arms (bilaterally treated subjects vs. unilaterally treated subjects).

Composite score and individual subscale scores from VFQ-25 will be summarized using descriptive statistics. Change from baseline at each visit for the composite score and individual subscales scores will be analyzed separately using a MMRM model, with adjustment for baseline score, as described in section 13.1.6.

36-Item Short Form Health Survey, Version 2 (SF-36v2)

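### Between-arm change in HVF pattern standard deviation is tested with no stated direction of benefit, although the index rises and then falls as dense field loss spreads

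*SAP*

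**What the plan says.** Protocol 16.4.2.2 gives examples of the HVF parameters to be used as secondary endpoints: "mean deviation, foveal threshold sensitivity, pattern standard deviation and others". For these it asks: "Adjusted difference between the treatment groups will be estimated at each post-treatment time point, along with the two-sided 95% CI and p-value".

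SAP 13.2.1 lists "Pattern standard deviation" as one of three HVF 30-2 parameters whose change from baseline is an efficacy variable. SAP 13.2.3 then directs: "The parameters detailed in sections 13.2.1 will be analyzed separately using a MMRM model, with adjustment for baseline score, as described in section 13.1.6". The model code in SAP 13.1.6 requests the difference between arms at each time point. The index is therefore tested, not only summarised.

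The one handling rule for HVF values, in SAP 13.2.1, is "If HVF is off then set to missing, if <0 set to 0". It does not say which HVF parameter it covers or what counts as off.

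The plan gives a direction of benefit for LogMAR (Protocol 16.4.1.5), VFQ-25 and SF-36 (SAP 13.2.1) and contrast-sensitivity response (SAP 13.3). It gives none for pattern standard deviation. It neither limits the index to a range of field severity nor asks for it to be read with mean deviation.

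**The concern.** Neither document defines the index, but its name makes it a standard deviation of the deviations across the points of one field. Such a quantity measures how uneven the loss is, not how much there is. It is low when nearly all points are intact and low again when nearly all are lost.

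New loss in an almost intact eye and recovery in an eye that had lost most of its field can then move the index the same way. Gains in eyes on opposite sides of the peak can cancel in the arm mean. What is at stake is the reading of one secondary contrast, which will carry a confidence interval and p-value at each visit with no multiplicity adjustment (SAP 6.3).

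**Working it through.** **Figures in the plan.** The documents state no expected value, SD or effect for this index. The only sample-size figure, 45 per group (Protocol 16.2), concerns LogMAR. With difference 0.3, SD 0.50, two-sided alpha 0.05 and 80% power, a t-based calculation gives 44.6, so 45, with power 80.4%. It reproduces and is not touched by this point.

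**Two-level field.** Let a fraction p of points be depressed by D dB and the rest be normal. Then

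- mean deviation = −D·p
- pattern standard deviation = D·√(p(1−p))

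D is not in the documents. I assume 30 dB and check 20 and 25 dB.

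| Points lost | Mean deviation, D = 30 | Pattern SD, D = 30 | Pattern SD, D = 25 | Pattern SD, D = 20 |
|---|---|---|---|---|
| 0% | 0 | 0 | 0 | 0 |
| 10% | −3 | 9.0 | 7.5 | 6.0 |
| 25% | −7.5 | 13.0 | 10.8 | 8.7 |
| 50% | −15 | 15.0 | 12.5 | 10.0 |
| 75% | −22.5 | 13.0 | 10.8 | 8.7 |
| 90% | −27 | 9.0 | 7.5 | 6.0 |
| 100% | −30 | 0 | 0 | 0 |

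At D = 30:

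- Recovery from 90% to 50% lost: mean deviation improves by 27 − 15 = 12 dB; the index rises by 15.0 − 9.0 = 6 dB.
- Recovery from 50% to 10% lost: mean deviation improves by 15 − 3 = 12 dB; the index falls by 15.0 − 9.0 = 6 dB.
- One eye of each kind: average gain in mean deviation 12 dB; average change in the index (6 − 6)/2 = 0.
- Loss from 10% to 90%: mean deviation worsens by 27 − 3 = 24 dB; the index does not change.

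For the first of these, D = 20 gives 8 dB better mean deviation with a 4 dB rise in the index, and D = 25 gives 10 dB with a 5 dB rise.

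**Baseline adjustment.** Eyes with 10% and 90% lost both start at 9.0 dB, yet recovery moves them in opposite directions. A covariate for the baseline value of the index cannot tell them apart.

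**Check on a test grid.** Protocol 12.5.4 specifies perimetry "using the 30-2 SITA Fast strategy, Stimulus III White". I took 76 points less 2 at the blind spot, leaving 74, and let a central scotoma grow outward with lost points at 0 dB. Assumed: peak sensitivity 31 to 33 dB, slope 0.15 to 0.35 dB per degree, points weighted equally or towards the centre.

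- The index peaks at 13.9 to 15.9 dB with 20 to 36 points lost (20/74 = 27%; 36/74 = 49%).
- With all 74 lost it is 1.1 to 2.7 dB, while mean deviation is about −26 to −31 dB.
- In one setting (peak 33 dB, slope 0.25, equal weights), going from 68 to 37 points lost improves mean deviation by 26.0 − 14.7 = 11.3 dB and raises the index by 14.9 − 7.9 = 7.0 dB.

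The sizes in dB depend on these assumptions. The rise and fall appears in every setting tried.

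**The case against.** The strongest objection is that the plan does not show any eye past the peak. Entry down to hand-motion vision (Protocol 10.2.3) concerns acuity, not field extent, and the expected defect is described as "central and cecocentral visual field defects", which suggests localised loss. No baseline mean deviation or count of lost points is given. If nearly all eyes stayed below the peak, the index would have a consistent direction. This stands: a reader might infer that primary eyes lie on both sides of the peak, but the documents do not support that as fact.

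A reader might also infer that total loss will be recorded as normal. That is too strong. A field floored at 0 dB keeps an index of about 1 to 3 dB in the grid check, so close to normal is the fair description. Some unmeasurable fields may also become missing under the rule in SAP 13.2.1, although that rule does not touch measurable fields that recover from extensive loss.

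Third, the index will not be read in isolation. Mean deviation and foveal threshold are analysed beside it, and SAP 13.2.1 also plans point-by-point gain and loss categories and field maps per eye. Under randomisation the test remains valid as a test of any difference. So it would be wrong to say the result cannot be interpreted at all. What remains is that the plan tests the index separately, states no direction and does not require the other measures to be used in reading it.

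**Conclusion.** The point holds as a minor one. Change in pattern standard deviation is tested between arms, yet the index is non-monotone in the extent of dense loss and has no stated direction of benefit. Under the assumed 30 dB depth, the same 12 dB gain in mean deviation can appear as a rise or a fall of 6 dB, depending on where the eye starts. The between-arm difference therefore has no assured direction of benefit on its own.

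This rests on reading the index, from its name, as a standard deviation across test points, and on loss being dense. The share of eyes affected is unknown. A reader might infer that the trial's main conclusion is at risk; it is not, because all of the type I error is assigned to the LogMAR primary endpoint (SAP 6.3) and no decision rule uses this index.

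**What to change.** - In SAP 13.2.1 and 13.2.3, keep mean deviation and foveal threshold sensitivity as the tested HVF parameters. Report pattern standard deviation descriptively, alongside or cross-tabulated with mean deviation, with no between-arm test on its change.
- Record this in SAP 3.4 as a departure from Protocol 16.4.2.2, and say that it was made after the 1.5-year analysis, since SAP version 10.0 post-dates it.
- Because this fix relies on mean deviation, state in SAP 13.2.1 that setting values below zero to zero does not apply to mean deviation. Read literally, the rule would turn every negative mean deviation into 0.

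The cost is SAP wording, one log entry and one fewer model. The downside is that a parameter the protocol names as an example becomes descriptive only.
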